9.2 Sample Size and Randomization

For the power estimation, this study will use the significance level of .05 with two-tailed test. This study will recruit 100 individuals assuming about 20% missing data due to unusable imaging data and dropouts. In the Primary Mechanistic Hypothesis (formerly connectivity portion of Hypothesis 1a), power was estimated by focusing on the functional connectivity between DLPFC and dACC as the Primary Mechanistic Outcome. According to one prior study (47), the change in connectivity between DLPFC and dACC from pre to post rTMS is change in the quite large ($d=0.69$). We have augmented this one finding with numerous findings from other rTMS connectivity and functional activity studies, which demonstrated quite large effect sizes (see table 3 and table 4 below). Therefore, a somewhat conservative effect size of $d=0.8$ is being utilized for this study. The change from baseline to post-stimulation will be negligible in the sham rTMS group. Given this scenario, with the usable sample of 80 (40 rTMS, 40 sham), the estimated power is 0.8 ($\alpha=.05$, two-sided). For the Relevant Clinical Hypothesis (formerly Hypothesis 2b) and Secondary Hypotheses E (formerly Hypothesis 2a) as well as Secondary Hypotheses A, C, and D, both effect sizes and p-values will be monitored, with more emphasis on gathering information on effect sizes.

Manuscript	Site of Stimulation	Functional Connectivity Pair	Effect Size
Eldaief et al	L Posterior Intraparietal Lobule	rpIPL<->mPFC	0.72
Eldaief et al	L Posterior Intraparietal Lobule	rpIPL<->PCC	0.62
Nettekoven	Primary motor cortex	Primary Motor Cortex<->Premotor Cortex	0.9
Halko et al	Lateral cerebellum	DMN<->Posterior cingulate	1.26
Valchev et al	Primary somatosensory	Premotor	0.79

Vercammen Watanabe et al	Temporal-Parietal-Junction	Temporal-Parietal-Junction<->Right Insula	1.33
Watanabe et al	Left Motor Cortex	Left Motor Cortex<-> Right Motor Cortex	1.79
Watanabe et al	Left Motor Cortex	Left Motor Cortex<-> Right Motor Cortex	2

Table 3: Effect sizes for rTMS induced changes in functional connectivity as a surrogate for hypnotizability (Hoeft 2012)(31) modulated by rTMS(54, 56, 57, 158-160).

Manuscript	Stimulation Site	MRI/PET	Effect Size
Hubl	Frontal Eye Field	BOLD	0.4242
Bestmann	Motor/Somatosensory cortex	BOLD	2.36686405
Bestmann	Motor/Somatosensory cortex	BOLD	2.30589176
Cho	Right Dorsolateral prefrontal cortex	PET (CBF)	1.70333333
Valchev	Motor/Somatosensory cortex	BOLD	2.86192037
Valchev	Motor/Somatosensory cortex	BOLD	1.23857467

Table 4: Effect sizes for rTMS induced changes in brain activity as a surrogate for hypnosis (Jiang 2016)(34) modulated by rTMS(159, 161-163).

As our study is a randomized controlled study, in line with the intention to treat principle, our primary analysis will be a straightforward comparison of the active versus sham groups using a linear model. Following the convention in imaging studies, we will conduct our primary analyses treating the contrast (baseline vs post) as one univariate outcome. The univariate model described below can be estimated either using linear regression or analysis of variance procedures.

A continuous outcome Y for individual i ($i=1,2,3,\dots, N$) can be expressed as $Y_i = \alpha + \gamma Z_i + \varepsilon_i$, where α is the mean of the sham group, Z_i is the randomized treatment assignment status (0=sham, 1=active), γ is the treatment effect, and $\varepsilon_i \sim N(0, \sigma^2)$. According to random assignment, the estimate of γ will be interpreted as causal effect of treatment assignment.

We do not expect much variation across our narrowly defined subjects, although some variation is still possible. As a way of sensitivity analysis, we will also analyze the data in the linear mixed effects modeling framework allowing for random intercepts, although this is not customary in imaging studies. The linear mixed effects model described below will be estimated using the maximum likelihood estimation method implemented in SPSS or in Mplus.

The outcome Y for individual i at time point t ($t = 1,2$ for pre and post) is now expressed as

$$Y_{it} = \eta_{0i} + \eta_{1i}W_t + \varepsilon_{it}, \quad (2)$$

$$\eta_{0i} = \eta_0 + \gamma_0 Z_i + \zeta_{0i} \quad (3)$$

$$\eta_{1i} = \eta_1 + \gamma_1 Z_i + \zeta_{1i} \quad (4)$$

where η_{0i} is the initial status and η_{1i} is the linear growth. The set of time scores W_t reflects the linear growth (0,1) for the pre and post assessments. The residual ε_{it} is allowed to vary across time, and is assumed to be normally distributed in our parametric estimation approach. The intercepts in (3)-(4) can be interpreted as the main initial status (η_1) and linear growth (η_2) for the sham group. The random effect residual ζ_{0i} is assumed to be normally distributed, whereas ζ_{1i} is fixed at zero as we only have two time point data. The effect of treatment on initial status (γ_0) will be fixed at zero in line with the random assignment. The estimate of γ_1 will be interpreted as causal effect of treatment assignment on the pre and post change in the outcome.

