All participants will undergo the ***Hypnotic Stroop Scan Session Day***. All participants will receive the identical pre-rTMS scan session. One-half (n=50) will receive active rTMS and one-half (n=50) will receive sham rTMS (two arm, double-blind, sham-controlled). All participants will receive the identical post-rTMS scan session. Changes in resting state *functional connectivity* between L-DLPFC and dACC in the active rTMS versus the sham rTMS conditions will be assessed. This primary endpoint is a between-group comparison. We will also measure the difference in brain *activation* during the hypnotic induction, and Stroop task (after post-hypnotic suggestion) between the active and sham rTMS. This will also be a between-groups comparison. Using the *Hypnotic Induction Profile (HIP)* and *Hypnotic Intensity Scale (HIS)*, we will compare the change in hypnotizability and hypnotic intensity score between the active and sham rTMS groups.

All participants will undergo the ***Hypnotic Analgesia Scan Session Day***. All participants will complete identical pre- and post- rTMS scan session. One-half will receive active rTMS and one-half will receive sham rTMS. Changes in resting state *functional connectivity* between L-DLPFC and dACC in the active rTMS versus the sham rTMS conditions will be assessed. This primary endpoint is a between-group comparison. This scan-session also addresses a secondary aim of determining the difference in functional connectivity within the hypnotic analgesia network between the active and the sham rTMS groups. This will be a between-groups comparison. We will also compare the activation within the hypnotic analgesia network between the active and sham rTMS groups. This will be a between-groups comparison. We will also utilize a perturbation technique to probe the hypnotic induction in an alternative way. Finally, we will compare the difference in pain thresholds between the active and sham rTMS groups.

Interventions and Duration

Intervention: We will compare active versus sham rTMS as a technique for modulating the neural

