9.6 Outcomes

9.6.1 Primary Outcomes

Primary Mechanistic Outcome Measure: *To determine the effect of active, inhibitory rTMS (cTBS) over L-DLPFC on modulating the connectivity of the neural network that underlies hypnotizability.*

This study will test an augmentation approach where one modality (rTMS) (30) is being used to modulate the neural circuitry underlying another technique (hypnotizability) in an effort that this combinatory approach may transiently produce the high hypnotizable phenotype on formal testing(31). It will be determined if modulation of the neural circuitry that underlies hypnotizability with rTMS can potentially produce a brain connectivity pattern that resembles a highly hypnotizable individual(31). This study proposes to measure the change in hypnotizability by contrasting the functional connectivity between the L-DLPFC and dACC at pre- and post-rTMS for both rTMS conditions (active versus sham cTBS) (31).

Hypnotizability Scans for Primary Outcome Measure: All participants will receive the same identical pre-rTMS resting state scan(31, 51). After randomization (to either active DLPFC rTMS or sham rTMS) where one half (n=45) will receive active DLPFC rTMS (cTBS), and one-half sham DLPFC rTMS (cTBS) (n=45)(30), all participants have their hypnotizability post-rTMS scan session(31, 51).

fMRI Preprocessing and Analysis: All fMRI data will be preprocessed and analyzed using FSL (FMRIB Software Library, version 5.0) (88). Physiological signals will first be removed using RETROICOR and RVHRCOR (97, 98). The first 6 volumes will be discarded to allow for signal stabilization. The following standard preprocessing steps will then be applied: motion correction using least square minimization (99), removal of non-brain tissues (100), resampling to 2 x 2 x 2 mm³ voxels, spatial smoothing with a 6 mm full-width at half-maximum (FWHM) Gaussian kernel to improve functional alignment between participants, and mean-based intensity normalization of all volumes by the same factor and high pass temporal filtering with a Gaussian-weighted least-squares straight line fitting, and linear registration using the FMRIB's Linear Registration Tool (FLIRT, 6 degrees of freedom (DOF)) to T1-weighted anatomical images and Montreal Neurological Institute (MNI) standard space.

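### The stated power of 0.8 does not follow from its inputs: d = 0.8 with 40 per arm at two-sided 0.05 gives 0.94 on the planned change-score comparison, and the SD unit of d is not given

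*Combined protocol and SAP*

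**What the plan says.** All of this comes from the combined protocol and SAP, section 9.2, unless noted.

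- **Error rate:** "For the power estimation, this study will use the significance level of .05 with two-tailed test".
- **Effect size:** "a somewhat conservative effect size of $d=0.8$ is being utilized for this study". It is justified by one earlier study of the same connection, with d = 0.69 for the pre-to-post change, and by the rTMS studies in Tables 3 and 4.
- **Sham arm:** "The change from baseline to post-stimulation will be negligible in the sham rTMS group".
- **Sample and power:** "with the usable sample of 80 (40 rTMS, 40 sham), the estimated power is 0.8".
- **Analysis:** a linear model of active versus sham in which "we will conduct our primary analyses treating the contrast (baseline vs post) as one univariate outcome". The model has one residual variance, that of the contrast.

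The section gives no SD, pre-post correlation, formula or software for the power figure. It does not say what standardises 0.8, 0.69 or the tabulated values. This is the only power figure in the plan. For the Relevant Clinical Hypothesis and Secondary Hypotheses A, C, D and E, section 9.2 says only that effect sizes and p-values will be looked at.

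**The concern.** Section 9.2 appears to state everything a two-group power calculation needs, yet the result it reports is well below what those inputs produce. Either one number is wrong or an assumption that decides the answer is missing. In both cases a reader cannot tell which effect the trial had 80% power to detect on its primary mechanistic outcome, and that is what is needed to interpret a null result.

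The missing unit makes this more than a slip. The outcome is a change score. An effect expressed in SDs of the change and one expressed in SDs of a single scan can differ considerably, depending on how strongly the two scans correlate.

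**Working it through.** **Inputs (section 9.2).** n = 40 per arm; two-sided alpha = 0.05; d = 0.8; sham change about zero, so the between-arm difference equals the change in the active arm; two-group comparison of the baseline-to-post contrast. The recruitment figure is consistent with 20% loss: 80 / (1 − 0.20) = 100.

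**Attempt to reproduce 0.8.** Take d in SDs of the change score, the residual SD of the model in 9.2, equal in both arms.

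- Noncentrality = d × √(n/2) = 0.8 × √20 = 3.578.
- Degrees of freedom = 2 × 40 − 2 = 78; critical t = 1.991.
- Power (noncentral t) = **0.942**.
- Normal approximation: Φ(3.578 − 1.960) = Φ(1.618) = 0.947.

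The stated 0.8 is not reproduced; the gap is about 14 percentage points.

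**Other figures found in the plan** (change-score SDs, two-sided 0.05):

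| d | n per arm | Power |
|---|---|---|
| 0.80 | 45 (sections 9.6.1 and 9.6.2) | 0.96 |
| 0.80 | 50 (Précis) | 0.98 |
| 0.69 | 40 | 0.86 |
| 0.62 (smallest value in Table 3) | 40 | 0.78 |

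The last row comes near, but the plan says that 0.8 was used. Changing the test does not help either. One-sided 0.05 gives 0.97, a paired test within 40 active participants gives over 0.99, and a Mann-Whitney test gives about 0.91 to 0.94.

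**What would give about 0.80.** Each route needs an input that the power statement does not contain:

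- d = 0.634 with 40 per arm: 0.80 (d = 0.63 gives 0.795).
- d = 0.8 with 26 per arm: 0.807.
- d = 0.8 with 40 per arm and alpha divided by 6: 0.805.
- d = 0.8 in raw-score SDs with pre-post correlation r = 0.2: 0.798.

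**Effect of the unit.** If d is in SDs of a single scan, and the SD is the same before and after, the effect in change-score SDs is d / √(2(1 − r)). For example, 0.8 / √(2 × 0.8) = 0.632. The documents give no r, so the values below are assumptions. Power with 40 per arm:

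| Assumed r | d = 0.80, raw-score SD | d = 0.69, raw-score SD |
|---|---|---|
| 0 | 0.70 | 0.58 |
| 0.2 | 0.80 | 0.67 |
| 0.5 | 0.94 | 0.86 |
| 0.7 | 0.995 | 0.98 |

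On this reading, power at d = 0.69 is below 0.80 when r is below 1 − (0.69/0.634)²/2, or about 0.41.

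**The claim that 0.8 is conservative.** The eight values in Table 3 sum to 9.41, so their mean is 1.18; their median is (0.90 + 1.26)/2 = 1.08. Five of the six values in Table 4 exceed 0.8. Against the tables, 0.8 is on the low side. Against 0.69 it is not, and none of the eight Table 3 rows is the DLPFC–dACC pair.

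**The case against.** The strongest reply is that an unstated unit cuts both ways: if d is in raw-score SDs and the pre-post correlation is about 0.205, power is 0.80 and the plan's figure is right. That is arithmetically correct, so 0.8 is not proved wrong on every reading. But neither the raw-score unit nor any correlation appears in the documents, while the analysis model in 9.2 points to the SD of the contrast. If that was the calculation, its deciding assumption was left out, and the section still needs correcting.

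The second reply is that little follows. On the change-score reading the plan understates its power, 0.69 still gives 0.86, and the separate SAP of January 2024 already describes collected data, so the sample size cannot move. This stands, and it limits the weight of the point. The range of 0.58 to 0.98 does rest on assumed correlations.

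Third, 0.94 is for one two-group test. The Précis names a primary connectivity comparison on each of two scan days, and section 9.7 adds a scan-order term. Neither restores 0.8: halving alpha for two days gives 0.90. It is still reasonable for the restated sentence to say that it refers to a single comparison.

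Finally, the word conservative can fairly be read as a comparison with Tables 3 and 4, where it holds. The plan also discloses the 0.69 openly.

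**Conclusion.** The concern holds. No set of inputs stated in the plan produces the stated power of 0.8. For the planned comparison of change scores, d = 0.8 with 40 per arm at two-sided 0.05 gives 0.94, assuming d is in change-score SDs, zero sham change and equal SDs in the two arms. On those terms 40 per arm has 80% power for about 0.63 SD.

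This does not show an underpowered trial, and it changes no analysis. The part with real uncertainty is the unit. Depending on it, power at the one on-target estimate (0.69) is 0.86, or anywhere from 0.58 to 0.98 over the assumed correlations. It should be corrected, as a matter of getting the primary sample-size statement right.

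**What to change.** Reword section 9.2 along these lines: *With 40 usable participants per arm and two-sided alpha 0.05, a single two-group comparison of the change score has 80% power for a between-arm difference of 0.63 SD of the change score, and 94% power for 0.80 SD of the change score.*

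Then:

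1. State the standardiser of the cited 0.69 and give its power conditionally. It is 0.86 in change-score SDs, with zero sham change and equal SDs. In raw-score SDs it is 0.58, 0.67, 0.86 and 0.98 for assumed pre-post correlations of 0, 0.2, 0.5 and 0.7.
2. Replace the description of 0.8 as conservative with the comparison itself: below the Table 3 mean and median, above the one DLPFC–dACC estimate.

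The cost is wording in 9.2 and a look at the source of the 0.69. No analysis changes.

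A separate consistency correction, with no bearing on the power figure, is to reconcile the arm sizes. Section 9.6.1 has "one half (n=45) will receive active DLPFC rTMS (cTBS"), and 9.6.2 repeats 45 under several secondary outcomes, whereas the Précis has "One-half (n=50) will receive active rTMS and one-half (n=50) will receive sham rTMS".

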3. STUDY DESIGN

This study is a double-blind, placebo-controlled, mechanistic trial assessing active rTMS as a strategy for the modulation of the neural circuitry underlying hypnotizability and hypnotic analgesia in participants with FMS (31). We will utilize the gold standard for blinded rTMS studies which utilizes a double-sided active/sham rTMS coil that allows for double blinding of the treater and the participant (Magventure Cool-B65 A/P Butterfly Coil)(86). All 100 participants will be randomized to one of the two stimulation arms (sham or active rTMS) and will go through both of the hypnotic stroop and hypnotic analgesia scan-session days. The only difference between these two groups is the application of active versus sham rTMS. Otherwise, all hypnosis interventions and MRI scans include the same structural and functional acquisitions.

[figure not shown]

Figure 2: This is a double blind, sham-controlled, counterbalanced, mechanistic trial. There will be 100 participants with a confirmed diagnosis of FMS recruited, enrolled, and randomized to one of the two arms (active or sham rTMS). The scan sessions will be counterbalanced to control for order effects.

Primary Mechanistic Objective: To determine the effect of active, inhibitory rTMS (continuous theta-burst stimulation-cTBS) over left dorsolateral prefrontal cortex (L-DLPFC) on modulating the neural network that underlies hypnotizability and hypnosis. **In other words, the Primary Mechanistic Outcome Measure** is the change in functional connectivity between the L-DLPFC and the dACC in active versus sham rTMS (cTBS), and the associated effect of inhibition of activity in the L-DLPFC on activity in the dACC.

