- Spectroscopy: Non-invasive magnetic resonance spectroscopy (MRS) will be used to quantitatively measure brain metabolites, including both inhibitory and excitatory neurotransmitters as well as markers of inflammation.

Pre-rTMS Stroop Assessment

Hypnotic Stroop and Non-Hypnotic Stroop Pre-rTMS Scan Session: This session includes all of the pre-rTMS questionnaires, behavioral evaluations and scans necessary to compare to the post-rTMS.

- Medication Washout, Drug Screen, Pregnancy Test Form: This form will be administered at the beginning of each pre-rTMS assessment to ensure medication washout compliancy (if applicable), document drug screen results, and screen for pregnancy (if applicable).
- Hypnotic Induction Profile: This administration of the HIP will serve as the baseline measure for comparison after the rTMS stimulation session(87). HIP will be measured on three separate occasions throughout the stroop assessment visit - 1) immediately following the pre-rTMS stroop MRI session, 2) immediately following rTMS, and, 3) immediately following the post-rTMS stroop MRI session.
- Stroop Task: This administration of the Stroop task will serve as the baseline measure for comparison to the post-rTMS session(32, 118).
- Pre-TMS Hypnotizability Scan Session (1 hour duration)
 - Structural Acquisition (T1): This structural scan is necessary for several reasons: demonstration that the participant's brain is structurally normal, imaging analysis, and rTMS targeting(81).
 - BOLD fMRI Acquisitions
 - Resting State: This is the baseline scan required for the primary endpoint. Individuals with high hypnotizability have been demonstrated to have higher functional connectivity between the dorsolateral prefrontal cortex and the dorsal anterior cingulate cortex (31).
 - Stroop Task: Brain activity while performing conflict tasks has been demonstrated to be different depending on a subject's level of hypnotizability. This baseline would demonstrate the subject's normal functional brain response to the Stroop Task

(32). Functional brain response to the stroop task will be measured following hypnosis (Hypnotic Stroop) and non-hypnosis (Non-Hypnotic Stroop) audio instructions. These acquisitions will be randomized to prevent order effects. Highly hypnotizable individuals can have a loss of the Stroop Effect with specific post-hypnotic instruction (119, 120) which correlates with the reduction in neural activity during conflict (35).

Pre-rTMS Analgesia Assessment

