9.7 Data Analyses

The Primary Mechanistic Outcome Measure for this study is increased functional connectivity between the L-DLPFC and dACC. The Relevant Clinical Outcome Measure is change in hypnotic analgesia as measured by change in pain thresholds. For secondary aims, the emphasis is on identifying the magnitude of effects (clinical significance, effect size) instead of statistical significance. We will test whether the change in connectivity from baseline to post-treatment is greater in the active rTMS group as compared to the sham group. Following the convention in imaging studies, we will conduct our primary analyses treating the contrast (baseline versus post) as one univariate outcome. We do not expect much variation across our narrowly defined subjects, although some variation is still possible. Given that, we will also analyze the data in the linear mixed effects modeling framework (165, 166) allowing for random intercepts (although this is not customary in imaging studies) as a way of sensitivity analysis. The same analytical strategy will be used to test the effect of rTMS on the DLPFC and dACC activity, which is Secondary

Hypothesis A (previously activity portion of Hypothesis 1a-in grant), activity during conflict task (Secondary Hypothesis C), and during post-hypnotic instruction conflict task (Secondary Hypothesis D).

We are using thermal pain stimuli percept-matched to the individual receiving the intervention. Examining the treatment-effect moderating the role of the pain level is not a primary aim of this project.

Moderator/mediator investigation: We will explore various baseline variables as potential moderators of rTMS effect. For this investigation, we will employ the McArthur approach (167, 168) for moderator analysis. We will also examine potential mediators of rTMS effect using the McArthur approach (167, 168) as well as contemporary causal mediation approaches (169-174), which we believe will provide valuable insights regarding the neuromodulation mechanism for the next phase of investigation.

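### The primary connectivity test compares raw pre-to-post contrasts by arm; baseline adjustment suited to the two scan days would be at least as precise in most settings, at little cost

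*Combined protocol and SAP*

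**What the plan says.** Section 9.2 defines the primary analysis as a linear model with an intercept and a 0/1 arm indicator, and says: "Following the convention in imaging studies, we will conduct our primary analyses treating the contrast (baseline vs post) as one univariate outcome". Section 9.7 repeats this: "Following the convention in imaging studies, we will conduct our primary analyses treating the contrast (baseline versus post) as one univariate outcome". Imaging convention is the main reason given. Section 9.2 also refers to a simple intention-to-treat comparison and to little expected variation between participants.

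Baseline connectivity enters a model only in a secondary role: "As a way of sensitivity analysis, we will also analyze the data in the linear mixed effects modeling framework allowing for random intercepts". That model sets the arm difference at baseline to zero, and its slope residual "is fixed at zero as we only have two time point data". Section 9.7 (handling of missing data) adds a multivariate two-day sensitivity analysis and a term for session order.

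The scans behind the contrast are not tied to one day. The Précis describes the connectivity comparison for both the Stroop day and the analgesia day, and for each says: "This primary endpoint is a between-group comparison". Section 6.2.2 says of the pre-stimulation resting scan, again under both days: "This is the baseline scan required for the primary endpoint". Section 9.6.1, under "Hypnotizability Scans for Primary Outcome Measure", points to the hypnotizability session only. The Figure 2 caption in Section 3 says: "The scan sessions will be counterbalanced to control for order effects".

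**The concern.** Regressing post minus pre on arm is the same as regressing post on arm with the baseline coefficient forced to 1. Estimating that coefficient gives a smaller variance unless the true slope is close to 1. The baseline scan is collected anyway, and the first day's pre scan precedes any theta-burst train, so it is a legitimate covariate. Low between-participant spread, which the plan expects, tends to mean a low pre-post correlation, and that is where a raw contrast loses most.

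At stake are a wider interval and somewhat lower power for the headline comparison. Validity is not at stake.

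The form of adjustment needs care here. Because day order is counterbalanced, a given session falls on day 2 for about half the participants, after they have already had one stimulation session. That day's own pre scan is then a post-randomization measurement and should not be used as a covariate. The first-day pre scan, for its part, is a poor stand-alone baseline for a post scan taken on another day.

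**Working it through.** **Inputs from Section 9.2.** Two-sided 0.05; 40 usable per arm; d=0.8; prior-study d=0.69; stated power 0.8.

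**Assumed, because the documents are silent.** Same-day pre-post correlation r; cross-day correlation c; k = post SD / pre SD.

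**The plan's own figure.** The noncentrality is d√(n/2) = 0.8 × √20 = 3.58 on 78 df, which gives power 94.2%. The stated 0.8 does not follow from its inputs; at 40 per arm it corresponds to d of about 0.634. With d=0.69, power is 86.2%. These values take d to be on the change SD.

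**(A) Outcome from first-day scans, same-day ANCOVA.** With pre SD 1, the contrast variance is proportional to 1+k²−2rk and the ANCOVA variance to k²(1−r²). At k=1 the ratio is (1+r)/2.

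| ANCOVA / contrast variance | r=0.2 | 0.5 | 0.7 | 0.9 |
|---|---|---|---|---|
| k=1 | 0.60 | 0.75 | 0.85 | 0.95 |
| k=1.3 | 0.75 | 0.91 | 0.99 | 0.92 |
| k=0.8 | 0.47 | 0.57 | 0.63 | 0.61 |

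Estimating one slope at N=80 multiplies these by 77/76 = 1.013. That is also the worst-case cost, reached when the true slope is exactly 1.

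Power at k=1, with 77 df and the 1.013 factor:

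| | Contrast | r=0.2 | 0.5 | 0.7 | 0.9 |
|---|---|---|---|---|---|
| d=0.8 | 94.2% | 99.5% | 98.2% | 96.8% | 95.0% |
| d=0.69 | 86.2% | 97.4% | 93.8% | 90.7% | 87.4% |

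**(B) Outcome session on day 2 for half the participants.** Keep the own-session contrast as outcome and add the first-day pre scan, session order and their interaction. At k=1, the covariance of the first-day pre scan with the contrast is r−1 for the day-1 half and c−c = 0 for the day-2 half. Only the first half gains, so the ratio is about [(1+r)/2 + 1]/2 = (3+r)/4 before the cost of the extra terms. That cost is 1.027 in simulation. At r=0.5: 3.5/4 × 1.027 = 0.90. Simulation (four scans per person, order balanced within arm, 50,000 trials per cell) gave the following at k=1:

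| r / c | 0.2/0.1 | 0.5/0.3 | 0.7/0.5 | 0.8/0.5 | 0.9/0.6 |
|---|---|---|---|---|---|
| Form (B) / contrast variance | 0.82 | 0.90 | 0.95 | 0.98 | 1.00 |
| Power, d=0.8 (contrast 94.2%) | 97.4% | 96.2% | 95.2% | 94.7% | 94.3% |
| Power, d=0.69 (contrast 86.2%) | 92.0% | 89.5% | 87.9% | 87.0% | 86.2% |
| First-day pre scan as sole baseline for the post scan | 0.62 | 0.85 | 1.07 | 1.47 | 2.21 |

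The last row is approximately [1−((r+c)/2)²]/[2(1−r)] × 1.013. At 0.9/0.6 this is 0.4375/0.2 × 1.013 = 2.22. Used that way, the first-day scan can more than double the variance. With unequal SDs, form (B) at 0.5/0.3 and 0.7/0.5 gives 0.98 and 1.01 for k=1.3, and 0.81 and 0.82 for k=0.8.

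**(C) Both days' contrasts averaged, adjusted for the first-day pre scan and order.** Relative to the unadjusted average, the ratios are 0.81, 0.89, 0.93, 0.96 and 0.99 in the same five cells.

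Null rejection was 0.048 to 0.053 in every simulated cell for every model.

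**The planned mixed model.** Its implied covariance matrix is τ²+σ₁² (pre), τ²+σ₂² (post) and τ² (covariance). With non-negative variances it can match ANCOVA on complete pairs only if the pre-post covariance lies between 0 and the smaller of the two variances. Over 60 data sets per cell, the estimates agreed within 0.0001 in 100% at r=0.5 and 0.7 (k=1), 98% at r=0.9 (k=1), 83% at r=0.7 (k=1.3), 2% at r=0.9 (k=1.3) and 3% at r=0.9 (k=0.8). At r=0.9, k=1.3 the covariance is 0.9 × 1.3 = 1.17, above the pre variance of 1, and the model falls back to the change score.

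**The case against.** The strongest reply is that little is at stake. The contrast is valid, power on the plan's own d is already about 94%, and every gain rests on assumed r, c and k. In form (B) only the day-1 half benefits, the gain vanishes at high correlation, and one cell shows a 1% loss. This all stands; it makes the point a modest precision improvement, not the repair of an error.

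Second, the sample is scanned on two days in order to gain power. If both days' contrasts are averaged, unadjusted power at d=0.8 is about 99.9% when the two contrasts are uncorrelated and 98.3% when they correlate 0.5 (99.1% and about 94% at d=0.69). This also stands: averaging leaves little power to gain, though the interval still narrows. But the plan does not say that the primary contrast is a two-day average, and its multivariate two-day model is only a sensitivity analysis.

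Third, the mixed model already uses baseline. In many settings it gives the ANCOVA answer. It is not the primary test, however, and it departs from ANCOVA when the correlation is high and the SDs differ. One could argue that the non-negativity bound is not written down, but Section 9.2 specifies normal random components, which implies it.

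**Conclusion.** The point holds, as one of efficiency only. The primary test fixes the baseline slope at 1 when a scan that could estimate it is already collected. With equal SDs, adjustment reduces the variance of the arm effect by 5% to 40% in the same-day form before the 1.3% cost, and by 0% to 18% in the two-day form with its cost included. The power gain at d=0.8 is about 1 to 5 points and 0 to 3 points respectively. It is larger if the true effect is nearer the prior study's 0.69: about 1 to 11 points and 0 to 6 points. The direction does not rest on any single correlation, because the worst-case loss is about 1.3% or 2.7% of variance; the size does, since r, c and k are not in the documents. Adjustment does nothing about carryover of day-1 stimulation into a day-2 contrast, which Section 9.7 addresses separately through session order.

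**What to change.** In Sections 9.2 and 9.7, name the session or sessions that supply the primary contrast, put baseline connectivity into the primary model, and keep the unadjusted contrast as a sensitivity analysis:

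- **Outcome from first-day scans:** ANCOVA of the post scan on arm and that day's pre scan.
- **Outcome session may fall on day 2:** the own-session contrast on arm, first-day pre scan, session order, and the interaction of the last two. No covariate is then measured after stimulation.
- **Both days averaged:** the mean contrast on arm, first-day pre scan and session order.

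State that the first-day pre scan is not to be used as the sole baseline for a day-2 post scan. Keep the mixed model as the prespecified sensitivity analysis, without describing it as equivalent to ANCOVA.

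Timing matters. The separate SAP, dated January 2024 and written in the past tense, shows that HIP has already been compared by arm; the documents do not say whether connectivity has. If it has not, the cost is a statement of the primary session plus one covariate (first form), three terms (second) or two terms (third), with session order already planned. If it has, leave the prespecified contrast as primary and report the adjusted analysis beside it, labelled post hoc. The mixed model needs no such label.
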